## **2.3 Outcome Variables**

Sensitivity of stationary head CT for the detection of a hemorrhage using a reader study is defined as the ability of readers (radiologists) to use the stationary head CT to predict hemorrhage using the clinical assessment at 3 months as the gold standard. The interpretation of the clinical data will be made by the study PI ([name]). A neuroradiologist ([name]) may re-interpret images as necessary at the request of the PI.

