#### 4.2.4 Reader Study

All images will be de-identified before inclusion within a reader study. We will perform a reader study with physician readers comparing the acquired imaging s-HCT images and conventional head CT. We hypothesize that the sensitivity of reader's in the interpretation of images from the s-HCT system will be similar to that of the conventional CT imaging. The paired images will be presented to five readers. Readers will be blinded to which imaging modality is being presented. There is, however, readers may be able to distinguish the imaging modality based on the images. Our readers will consist of a trauma surgeon, neurosurgeon or neuro radiologist and non-study radiologists to better reflect the different clinical backgrounds that may be available in a Role 3 environment.

Reconstructed images will be presented in a clinical PACS environment. The readers will be presented images for interpretation in a two-phase study with an interim washout period. First, for each patient, either the s-HCT or conventional head CT images will be presented in random order, and the readers will be asked to identify the presence of hemorrhage (yes/no), the location of the pathology if present and confidence level (0 through 100% in 10% increments). Readers will also be asked to perform interpretations with the appropriate Imaging CT CDE, including the Marshall CT TBI classification code 30, hemorrhage and fracture elements. Four weeks later, the other modality for each patient will be presented in a random order and the same scoring obtained.

The scoring scheme used by readers will include 1) hemorrhage (yes/no) with confidence 0-100% in 10% increments, 2) fracture (yes/no) with confidence 0-100% in 10% increments, 3) streak artifacts (yes/no), and ) other artifacts (yes/no).

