### 7.2 Sample Size Rationale

[figure not shown]
For an equivalence test of the difference between conventional HCT and s-HCT, a sample size of 25 subjects achieves at least 80.0% power at a significance level of 0.050 when the lower equivalence difference is -0.237, the upper equivalence difference is 0.237, sensitivity of conventional HCT and s-HCT is assumed to be 90.0%, and the proportion of concordant pairs is assumed to be 0.900.

A table of power calculations for various values of N and various equivalence differences is shown below. For reference, a recent review of the sensitivity of skull radiographs to intracerebral hemorrhage gives a sensitivity range of 3 to 75%.

Power	N	Lower Equivalence	Upper Equivalence	CHCT Sensitivity	s-HCT Sensitivity	Concordance	Alpha
0.99969	25	-0.4	0.4	0.9	0.9	0.9	0.05
1	50	-0.4	0.4	0.9	0.9	0.9	0.05
1	75	-0.4	0.4	0.9	0.9	0.9	0.05
1	100	-0.4	0.4	0.9	0.9	0.9	0.05
0.99906	25	-0.38	0.38	0.9	0.9	0.9	0.05
1	50	-0.38	0.38	0.9	0.9	0.9	0.05
1	75	-0.38	0.38	0.9	0.9	0.9	0.05
1	100	-0.38	0.38	0.9	0.9	0.9	0.05
0.9974	25	-0.36	0.36	0.9	0.9	0.9	0.05
1	50	-0.36	0.36	0.9	0.9	0.9	0.05
1	75	-0.36	0.36	0.9	0.9	0.9	0.05
1	100	-0.36	0.36	0.9	0.9	0.9	0.05
0.99346	25	-0.34	0.34	0.9	0.9	0.9	0.05
1	50	-0.34	0.34	0.9	0.9	0.9	0.05
1	75	-0.34	0.34	0.9	0.9	0.9	0.05

1	100	-0.34	0.34	0.9	0.9	0.9	0.05
0.98497	25	-0.32	0.32	0.9	0.9	0.9	0.05
0.99999	50	-0.32	0.32	0.9	0.9	0.9	0.05
1	75	-0.32	0.32	0.9	0.9	0.9	0.05
1	100	-0.32	0.32	0.9	0.9	0.9	0.05
0.96829	25	-0.3	0.3	0.9	0.9	0.9	0.05
0.99996	50	-0.3	0.3	0.9	0.9	0.9	0.05
1	75	-0.3	0.3	0.9	0.9	0.9	0.05
1	100	-0.3	0.3	0.9	0.9	0.9	0.05
0.93837	25	-0.28	0.28	0.9	0.9	0.9	0.05
0.99979	50	-0.28	0.28	0.9	0.9	0.9	0.05
1	75	-0.28	0.28	0.9	0.9	0.9	0.05
1	100	-0.28	0.28	0.9	0.9	0.9	0.05
0.88916	25	-0.26	0.26	0.9	0.9	0.9	0.05
0.99902	50	-0.26	0.26	0.9	0.9	0.9	0.05
1	75	-0.26	0.26	0.9	0.9	0.9	0.05
1	100	-0.26	0.26	0.9	0.9	0.9	0.05
0.81472	25	-0.24	0.24	0.9	0.9	0.9	0.05
0.99623	50	-0.24	0.24	0.9	0.9	0.9	0.05
0.99996	75	-0.24	0.24	0.9	0.9	0.9	0.05
1	100	-0.24	0.24	0.9	0.9	0.9	0.05
0.71079	25	-0.22	0.22	0.9	0.9	0.9	0.05
0.98761	50	-0.22	0.22	0.9	0.9	0.9	0.05
0.99969	75	-0.22	0.22	0.9	0.9	0.9	0.05
0.99999	100	-0.22	0.22	0.9	0.9	0.9	0.05
0.57643	25	-0.2	0.2	0.9	0.9	0.9	0.05
0.96515	50	-0.2	0.2	0.9	0.9	0.9	0.05
0.99816	75	-0.2	0.2	0.9	0.9	0.9	0.05
0.99993	100	-0.2	0.2	0.9	0.9	0.9	0.05

Here is a plot as a function of N and the equivalence difference.

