### 7.3 Data Analysis Plans

We will estimate the sensitivity and specificity from the two modalities. To compare the results from the two imaging modalities, we will adopt the mixed effect ANOVA based on the Dorfman-Berbaum-Metz method. To test the main hypothesis, the F-test statistic from the model parameter estimates will be used to compare the mean sensitivity / specificity metrics between the conventional head CT and the simulated solid-state head CT. Possible interactions between the modalities and the readers and the hemorrhage type/locations will also be included and tested for statistical significance. Sensitivity and specificity on the presence of clinically actionable pathology will also be assessed, based on consensus read of the conventional imaging.

For each confidence comparison, the average confidence scores and the corresponding standard deviations will be reported. To test whether the mean

confidence score is larger than zero, a linear mixed effect will be used to analyze data, where the outcome variable is the confidence scores collected in this study and only a grand mean parameter is in the independent list. Additionally, a random intercept is used in the model to account for the correlation among readers when reading the images from the same patient. The Wald's test based on model fit will be used to test whether the grand mean parameter is larger than zero. When the p-value from this test is less than 0.05, it will be concluded that there exists significant evidence that readers have more confidence with the s-HCT modality compared to the other modality. ROC curves will be evaluated.

We will also descriptively compare inter-reader agreement by modality for image quality, confidence in image interpretation, presence and location of hemorrhage, and presence and location of fractures by computing and reporting Fleiss' kappa.

All statistical estimates of population parameters will be tabulated along with corresponding confidence intervals (CIs) and/or standard errors (SEs) to convey levels of precision / imprecision. Hypothesis tests that are deemed to be not statistically significant will be indicated as inconclusive.

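### Sensitivity and specificity for actionable pathology are scored against conventional CT, one of the two compared tests; report percent agreement instead (minor)

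*Combined protocol and SAP*

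**What the plan says.** Section 7.3 (Data Analysis Plans) begins: "We will estimate the sensitivity and specificity from the two modalities". It then compares conventional CT with s-HCT by an F-test. The same paragraph ends with a further endpoint: "Sensitivity and specificity on the presence of clinically actionable pathology will also be assessed, based on consensus read of the conventional imaging". The plan does not define actionable pathology. It does not say who forms the consensus, or whether they are separate from the five readers. It does not say whether one or both modalities are scored against it. The reader form in section 11 has no item for it.

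Section 4.2.4 describes the reader study as "comparing the acquired imaging s-HCT images and conventional head CT", with five readers seeing both modalities.

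The primary endpoint uses a different reference. Section 2.3 defines hemorrhage sensitivity "using the clinical assessment at 3 months as the gold standard", and section 4.2.3 collects the record for hemorrhage and fracture over those three months. On who assigns that truth, section 2.3 states: "The interpretation of the clinical data will be made by the study PI". It adds that a neuroradiologist "may re-interpret images as necessary at the request of the PI".

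**The concern.** An accuracy estimate needs a reference that stands apart from the tests it judges. Here the reference is a read of one of them. A case that conventional CT gets wrong can be wrong in the consensus too. A conventional read that repeats the error then counts as correct, and an s-HCT read that is right counts as wrong.

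Two outcomes are possible. If s-HCT alone is scored, an agreement figure is published as accuracy. If both are scored, part of any s-HCT deficit comes from the choice of reference. The endpoint is supplementary: it is not among the objectives in sections 2.1 and 2.2.

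**Working it through.** **The plan's own figure.** Section 7.2 gives at least 80.0% power for 25 subjects and a margin of 0.237. For a paired score test at 0.05 per side, power = 2Φ[(δ√n − 1.645·s_R)/s] − 1, where s² = 0.10 is the discordance. The restricted standard deviation s_R is 0.4735 (restricted discordant probability 0.0217, so s_R² = 2(0.0217) + 0.237 − 0.237² = 0.224). Then (1.185 − 0.779)/0.3162 = 1.284, and the power is 0.801. The figure reproduces. It does not involve the consensus read, so this point leaves it unchanged.

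**Direction.** Let π be prevalence, A and B the sensitivity and specificity of the consensus, Se and Sp those of a read, and c1 and c0 the covariance of read and consensus in true positives and true negatives.

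Apparent sensitivity = [π(Se·A + c1) + (1−π)((1−Sp)(1−B) + c0)] / [πA + (1−π)(1−B)].

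If both modalities have the same Se and Sp, everything cancels from the gap except the covariances:

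Gap = [π(c1 conventional − c1 s-HCT) + (1−π)(c0 conventional − c0 s-HCT)] / [πA + (1−π)(1−B)].

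The gap is zero if the consensus is error-free. It is also zero if consensus errors are unrelated to conventional reads beyond the case difficulty that both modalities share. Otherwise it favours conventional CT.

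**One value by hand (all inputs assumed except Se).** Take π = 0.5, Se = Sp = 0.90, A = 0.95, B = 0.98, error correlation 0.3 for conventional CT and 0 for s-HCT.

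- c1 = 0.3·√(0.09 × 0.0475) = 0.0196; c0 = 0.3·√(0.09 × 0.0196) = 0.0126.
- Denominator = 0.475 + 0.010 = 0.485.
- Apparent s-HCT sensitivity = (0.4275 + 0.001)/0.485 = 0.884.
- Gap = 0.5(0.0196 + 0.0126)/0.485 = 0.033, so conventional CT appears as 0.917.

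With a weaker consensus (A = 0.90, B = 0.95) the gap is 0.049; with a perfect one it is 0.

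**Illustration tied to section 7.2.** From that section: "sensitivity of conventional HCT and s-HCT is assumed to be 90.0" per cent, and "the proportion of concordant pairs is assumed to be 0.900". Both are given there for hemorrhage; applying them per reader to this endpoint is an assumption. Also assumed: 90% specificity, the same concordance in negatives, majority-vote consensus, and prevalence of 20-65%.

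In a probit model with residual variance 1, concordance of 0.900 needs a between-modality latent correlation of 0.737. Image-specific variance i runs from 0 to 2, with shared case variance (0.737/0.263)(1+i), which is 2.80 at i = 0 and 8.39 at i = 2 (unrounded inputs). Numerical integration gives a consensus that is 90.6-92.2% accurate, barely better than one reader, and:

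| Prevalence | Sensitivity gap, same five readers (points) | Gap, separate three-reader panel (points) | Apparent s-HCT sensitivity, either consensus |
|---|---|---|---|
| 20% | 4.0-11.5 | 0-8.8 | 82.2-86.9% |
| 35% | 2.7-7.8 | 0-6.0 | 87.7-90.4% |
| 50% | 2.0-5.9 | 0-4.5 | 90.5-92.2% |
| 65% | 1.6-4.7 | 0-3.6 | 92.3-93.2% |

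If s-HCT alone is scored, the error against a true 90% runs from −7.8 to +3.2 points. Specificity gaps mirror these: with the same five readers at 35% prevalence, the maximum is 4.7 points for specificity and 7.8 for sensitivity.

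**Primary truth labels.** Assume 25 positive patients and 90% sensitivity, so an average of 22.5 detected. Removing a case that all readers missed gives 22.5/24 = 93.75% (+3.75 points). Removing one that all detected gives 21.5/24 = 89.6% (−0.4). Adding one that all missed gives 22.5/26 = 86.5% (−3.5). A relabel can move the estimate either way.

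**The case against.** Section 7.3 names its reference openly, so nothing is hidden; the issue is mostly one of label. The endpoint is outside the stated objectives and no power is claimed for it. All of that stands and keeps the point minor.

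The sizes are also soft. They depend on a majority vote that mislabels about 8-9% of cases, on an assumed prevalence, and on a concordance borrowed from hemorrhage. The plan specifies no voting rule and no panel. That stands too: the figures illustrate a mechanism and do not forecast a result.

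Stronger readings are tempting, and the documents do not support them:

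- A reader might infer that the plan tests s-HCT against conventional CT on this endpoint. No such test is written for it; the text merely does not exclude one.
- A reader might infer that the primary analysis uses the conventional-CT consensus as truth. It does not; section 2.3 names the 3-month clinical assessment. That assessment may itself draw on conventional CT in the record, but the documents do not settle how far.
- A reader might infer that primary truth labels will be altered once results are known. Nothing says so. The table in section 4.3 puts the reader study at the end of data collection, and section 5.1 keeps research images out of clinical decisions. What remains is that no blinding of the label and no lock are stated.

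**Conclusion.** The point holds as a minor one. Calling the result sensitivity and specificity is wrong whichever way the sentence is read: it yields agreement with conventional CT, or a contrast tilted toward conventional CT. The tilt follows from the design unless the consensus is error-free or its errors bear no special relation to the conventional reads. Its size does not follow from the documents. Under the stated assumptions it is 1.6-11.5 points with the same five readers and 0-8.8 with a separate panel, and less with a better consensus. Sample size, alpha and power are untouched.

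The remark on primary truth labels is secondary. It rests on the silence of section 2.3 and would not carry a finding alone.

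**What to change.** In section 7.3, report this endpoint as positive and negative percent agreement of s-HCT with the conventional-CT consensus. State that conventional CT is not scored against that consensus and that no modality comparison is made on it. This takes one sentence or two and no new data or patients. The cost is a less favourable label on a supplementary result, and no contrast between modalities there.

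As a secondary safeguard in section 2.3, finalise each patient's 3-month truth label blinded to s-HCT images and reader scores. Complete any neuroradiologist re-read by then, and do both before reader data are opened. This costs one database-lock step.

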## **2.2 Secondary Objectives**

- To estimate specificity of stationary head CT for the detection of a hemorrhage using a reader study.
- To estimate sensitivity of stationary head CT for the detection of a fracture using a reader study.
- To estimate specificity of stationary head CT for the detection of a fracture using a reader study.
- To evaluate the reader confidence for the stationary head CT in detecting hemorrhage or fracture as compared to a conventional CT.

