## 11.0 APPENDICES

**READER STUDY:** Evaluation of a Carbon Nanotube Enabled Solid-State Head CT

Subject ID: \_\_\_\_\_

Reader: \_\_\_\_\_

Date: \_\_\_\_\_

1) Hemorrhage: \_\_\_\_\_ Yes \_\_\_\_\_ No  
Hemorrhage confidence 0-100% in 10% increments: \_\_\_\_\_ %  
Location (lobe): \_\_\_\_\_

2) Fracture: \_\_\_\_\_ Yes \_\_\_\_\_ No  
Fracture confidence 0-100% in 10% increments: \_\_\_\_\_ %  
Location (bone): \_\_\_\_\_

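### Section 7.3 summarizes and tests reader confidence without using reference status or correctness of the call, so the result measures certainty rather than confidence in detecting.

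*Combined protocol and SAP*

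**What the plan says.** The secondary objective in section 2.2 is "To evaluate the reader confidence for the stationary head CT in detecting hemorrhage or fracture as compared to a conventional CT".

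Section 4.2.4 has each reader record "hemorrhage (yes/no) with confidence 0-100% in 10% increments", and the same for fracture. The form in section 11.0 prints "Hemorrhage confidence 0-100% in 10% increments" under a yes/no box. Neither place says whether the percentage is certainty in the call just made or the probability that a bleed is present.

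For each confidence comparison, section 7.3 says that "the average confidence scores and the corresponding standard deviations will be reported". It then fits a linear mixed model. In that model "the outcome variable is the confidence scores collected in this study" and "only a grand mean parameter is in the independent list"; further, "a random intercept is used in the model to account for the correlation among readers when reading the images from the same patient". A Wald test asks whether the grand mean exceeds zero. A p-value below 0.05 is read as showing that "there exists significant evidence that readers have more confidence with the s-HCT modality compared to the other modality".

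Elsewhere, section 4.2.3 obtains reference status for both findings from three months of medical records. Section 7.3 also compares sensitivity and specificity between modalities. It mentions ROC curves in one line, with no rating variable, area measure or modality contrast.

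**The concern.** Confidence is recorded beside a yes/no call, so a very certain negative call on a patient who is bleeding earns a high score. A model with an intercept and a patient effect has no place for reference status or for whether the call was right. Section 3.1.2 admits patients with head trauma, known hemorrhage or skull fracture, so patients with and without each finding can be enrolled, and nothing in the model separates them.

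What comes out is average certainty. The objective speaks of confidence in detecting, and the two can diverge. If s-HCT images hide subtle bleeds so that readers call them absent without hesitation, mean confidence can rise while detection falls. The planned conclusion would then credit s-HCT with more confidence, and no planned table would show how that came about.

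**Working it through.** **1. The plan's own figure.** No power, effect size or expected score is given for confidence. The only power figure, in section 7.2, concerns equivalence of paired sensitivities: N = 25, margin 0.237, alpha 0.05, both sensitivities 0.90, concordance 0.90. The asymptotic paired score test gives power = 2Φ[(√N × margin − 1.645 s0)/s1] − 1, where s0 and s1 are the standard deviations of the paired difference under the null and the alternative. The result is 0.80108, which matches the stated 80%. It does not bear on confidence, so every confidence score below is an assumption.

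**2. Illustration in patients with hemorrhage.** Mean confidence = (share correct × score when correct) + (share wrong × score when wrong).

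- Conventional CT: 0.95 × 85 + 0.05 × 60 = 80.75 + 3.00 = 83.75.
- s-HCT, confident misses: 0.80 × 85 + 0.20 × 90 = 68 + 18 = 86.0.
- s-HCT, hesitant misses: 0.80 × 85 + 0.20 × 60 = 68 + 12 = 80.0.

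In both s-HCT cases 15 percentage points more bleeds are missed. The mean points the wrong way in the first and the right way in the second.

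**3. Break-even.** Solve 68 + 0.20x = 83.75: x = 15.75/0.20 = 78.75. The reversal needs s-HCT misses scored above this.

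**4. Pooling patients with and without hemorrhage.** Assumptions: conventional sensitivity 0.90; specificity 0.90 in both modalities; score 80 on correct calls and 50 on false positives in both; score on misses 50 (conventional) and 90 (s-HCT). The conventional mean is 0.90 × 80 + 0.10 × 50 = 77.0 in either group. At s-HCT sensitivity 0.70 the s-HCT mean in positives is 0.70 × 80 + 0.30 × 90 = 83.0, so the pooled difference is prevalence × 6.0. For contrast, the last column counts a score as positive if the call was right and negative if wrong.

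| s-HCT sensitivity | Prevalence | Pooled difference | Difference signed by correctness |
|---|---|---|---|
| 0.70 | 0.3 | +1.8 | −11.4 |
| 0.70 | 0.5 | +3.0 | −19.0 |
| 0.70 | 0.9 | +5.4 | −34.2 |
| 0.50 | 0.3 | +2.4 | −21.6 |
| 0.50 | 0.5 | +4.0 | −36.0 |
| 0.50 | 0.9 | +7.2 | −64.8 |

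The break-even depends on the assumptions: here, at sensitivity 0.70, 56 + 0.30x = 77 gives x = 70.

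**5. Simulation of the test.** 50 patients, 5 readers, prevalence 0.5, scores as in step 4 with patient SD 7 and reading SD 10, rounded to tens and held within 0 to 100. The grand-mean test was applied to s-HCT minus conventional differences at one-sided 0.05.

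| s-HCT sensitivity | s-HCT misses scored 90: declared more confident | s-HCT misses scored 50: declared more confident (mean difference) |
|---|---|---|
| 0.90 | 52% | 4% (−0.1) |
| 0.70 | 77% | 0% (−2.9) |
| 0.50 | 93% | 0% (−6.0) |

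Runs: 1000 per cell in the first column of results, 500 in the second. When the raw s-HCT scores were tested against zero instead, which is how the outcome is literally worded, the test was significant in 100% of runs. That is a separate defect, but it means the outcome has to be defined before anything else is repaired.

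**6. Correct calls in positives only.** In the step 2 illustration this gives 85 against 85. The 15-point loss disappears.

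**The case against.** Several points on the other side stand.

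- **Accuracy is assessed elsewhere.** Hemorrhage sensitivity is the primary objective, and section 7.3 compares it between modalities. The additional misses enter that comparison whatever the confidence result shows. Counting them does not guarantee that they are flagged: a loss of 0.15 lies inside the 0.237 margin used in section 7.2.
- **The reversal is conditional.** The first illustration changes both sensitivity and the certainty of misses. With hesitant misses the planned mean points the right way, and nothing in the documents says how confident misses will be.
- **The scale is unanchored.** If readers enter the probability of hemorrhage, a confident miss scores near zero and lowers the mean. The pooled mean then follows case mix and is no easier to interpret, but the mechanism above does not apply.
- **The objective is not restricted to correct calls.** Average certainty is a legitimate quantity. This argues for labeling it as certainty, not for leaving the conclusion as worded.
- **Pooling is inferred.** It follows from an intercept-only model on all collected scores. The plan may intend separate comparisons for hemorrhage and fracture, but nothing separates by reference status or correctness.

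The ROC line is a partial answer only. As written it specifies nothing and does not alter the rule for concluding greater confidence.

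A reader might infer that the plan makes a scanner look better overall for missing bleeds. The documents do not support that: one secondary endpoint is involved, misses count against s-HCT in the primary comparison, and the reversal rests on assumed scores.

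**Conclusion.** The point holds in limited form. The confidence analysis cannot separate confident detection from confident misses, so its conclusion does not answer the objective as worded. It could favor s-HCT while s-HCT misses more bleeds only if the percentage means certainty in the call and s-HCT misses are confident: above 78.75 in the first illustration and above 70 in the second at sensitivity 0.70. With s-HCT misses at 90 and sensitivity 0.70 against 0.90, the pooled gain is 3.0 points, ranging from 1.8 to 5.4 over prevalence 0.3 to 0.9. These sizes are illustrative because the documents give no confidence values. The issue is confined to the secondary confidence endpoint and is worth correcting because the correction is cheap.

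**What to change.** In section 7.3:

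- Define the outcome as the paired s-HCT minus conventional confidence difference. Report it separately for reference-positive and reference-negative patients, and for hemorrhage and fracture.
- Tabulate confidence for correct and incorrect calls by modality, with all reference-positive reads alongside. Stratifying by reference status alone is not enough: the 86.0 against 83.75 result arises entirely within positives.
- Specify the ROC analysis already mentioned: a rating built from the call plus its confidence, and the area under the curve by modality. Name it as the measure that links confidence to accuracy.
- Limit any conclusion of more confidence to certainty, read beside these tables. Do not base it on positives with correct calls, because that subset discards the misses and differs between modalities. Any high-confidence cut-off, such as 80%, should be descriptive only.

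In section 4.2.4 and on the form in section 11.0, state that the percentage is certainty in the call.

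The calls, scores and reference status are already collected. The cost is a few extra tables and fewer reads per estimate. The changes should be fixed before the reads begin, so that the choice of summary is not made after seeing them.

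### The reader-confidence test asks whether 0-100% scores average above zero, yet reads p<0.05 as more confidence with s-HCT than with the other modality

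*Combined protocol and SAP*

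**What the plan says.** The last secondary objective in Section 2.2 is comparative: "To evaluate the reader confidence for the stationary head CT in detecting hemorrhage or fracture as compared to a conventional CT".

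Section 4.2.4 collects a "confidence level (0 through 100% in 10% increments") for each image set. After the washout, "Four weeks later, the other modality for each patient will be presented in a random order and the same scoring obtained". The reader form in Section 11.0 has the same field ("Hemorrhage confidence 0-100% in 10% increments") and a matching one for fracture. Each modality therefore gets its own absolute, non-negative rating. No section defines a difference or a signed comparative score.

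Section 7.3 then specifies the analysis:

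- **Descriptive summary:** "For each confidence comparison, the average confidence scores and the corresponding standard deviations will be reported".
- **Model:** a linear mixed model "where the outcome variable is the confidence scores collected in this study and only a grand mean parameter is in the independent list", plus a random intercept for correlation among readers of the same patient's images.
- **Test:** a Wald "test based on model fit will be used to test whether the grand mean parameter is larger than zero".
- **Conclusion when p<0.05:** "it will be concluded that there exists significant evidence that readers have more confidence with the s-HCT modality compared to the other modality".

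**The concern.** The hypothesis tested and the conclusion drawn concern different quantities. A mean of zero represents equal confidence only if the outcome is a difference between modalities. For a score that cannot fall below zero, the mean is zero only if every reader records 0% for every image. The model has no modality term that could carry a comparison.

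Followed literally, the rule would report an advantage for s-HCT with almost any data set, including one in which readers were less confident with it. That would be a false statement on a listed objective. The primary sensitivity analysis is not touched.

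**Working it through.** **Inputs from the documents.** There are 50 patients (Sections 1.1 and 4.2.1) and five readers (Section 4.2.4). Scores run from 0 to 100 in steps of 10. The threshold is p<0.05; sidedness is not stated, although the form of the hypothesis suggests one-sided. No mean or SD of confidence is given anywhere.

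**The plan's own figure.** No power figure is given for the confidence test. The one in Section 7.2 concerns sensitivity: at least 80.0% power with 25 subjects and margins of ±0.237. Two one-sided score tests for paired proportions, with discordance 1 − 0.900 = 0.10 split evenly, give 0.8011. The figure reproduces and is not affected by this point.

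**Two literal readings of the outcome.**

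1. Scores from both modalities are pooled. Swapping the modality labels leaves the data set, and so the Wald z, unchanged. The statistic cannot favour either modality.
2. Only s-HCT scores are used. Conventional CT never enters the calculation.

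Neither reading can support a statement about the other modality.

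**A bound that needs no SD.** Let m be the grand mean in % and n the number of patients, with complete data. Each patient's mean lies between 0 and 100, so:

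- sample variance of patient means ≤ [n/(n−1)] × m(100−m)
- variance of the grand mean ≤ m(100−m)/(n−1)
- z ≥ m / √[m(100−m)/(n−1)] = √[(n−1)m/(100−m)]

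Setting the bound equal to a critical value c gives m = 100k/(1+k), where k = c²/(n−1).

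- n = 50, one-sided: k = 1.645²/49 = 0.0552, so m = 5.2%.
- n = 50, two-sided: k = 1.96²/49 = 0.0784, so m = 7.3%.
- n = 25, one-sided: k = 1.645²/24 = 0.1128, so m = 10.1%.
- n = 25, two-sided: k = 1.96²/24 = 0.1601, so m = 13.8%.

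The n = 25 case shows only what happens with half the patients; Section 7.2 uses 25 for a different endpoint. Above these means, rejection is certain. For example, at n = 50 and m = 70%, z is at least √(49 × 70/30) = 10.7.

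**Illustration with assumed SDs.** Assumed: patient SD 10, patient-by-modality SD 10, reader-by-modality SD 5, residual SD 15. Scores were rounded to tens and kept within 0-100, with 50 patients, five readers and 5,000 simulated trials per row.

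| True mean, s-HCT vs conventional | s-HCT declared better | Smallest z, pooled | Smallest z, s-HCT only |
|---|---|---|---|
| 70 vs 70 | 100% | 28 | 24 |
| 60 vs 80 | 100% | 29 | 19 |
| 10 vs 95 | 100% | 25 | 5.7 |

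The 100% holds for both readings. A second set of assumptions used conventional means of 20, 50 or 80, s-HCT equal or 20 points lower, SDs of 15 (patient), 8 (patient-by-modality) and 15 (residual), and 25 or 50 patients. It also gave 100% throughout, with a smallest z of 2.5.

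**What a comparative outcome does.** Two-sided false-positive rates at 70 vs 70, under the first set of SDs:

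| Analysis | Reader-by-modality SD 0 | Reader-by-modality SD 5 |
|---|---|---|
| Paired difference, patient intercept only | 5.0% | 23% |
| Paired difference, reader random effect, Satterthwaite df | 5.2% | 5.9% |
| Raw scores, modality fixed effect, patient intercept only | 21.5% | 42% |

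At 60 vs 80, the paired analysis with a reader effect declared s-HCT better in 0% of trials.

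**The case against.** The strongest reply is that a paired difference was plainly meant. The paragraph opens by referring to comparisons, fits only a mean, tests it against zero and concludes about one modality relative to the other. That is the shape of a one-sample test on differences, and Section 4.2.4 collects the pairs it needs. On that reading the plan lacks only a definition. This is probably the intention, but Section 7.3 does name the outcome, and it names the collected scores. An analyst following the text gets the wrong test, so the text has to change either way.

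Second, the reported means and SDs would let a reader notice a contradiction. They would, but they do not replace the pre-specified conclusion rule.

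Third, this is one secondary objective, and the primary analysis and sample size stand. That is correct and limits the scope.

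Fourth, the simulation SDs are invented, and 10 vs 95 is extreme. True, but the main result rests on the bound, which needs no SD. What does depend on the assumptions is the case for a reader effect: with no reader-by-modality variation, a patient intercept alone holds 5.0%. With five readers of deliberately mixed backgrounds, assuming none would be hard to justify.

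Finally, the documents do not say whether confidence means certainty in the yes/no answer or likelihood that the pathology is present. That point stands. Under the second meaning, a positive difference would not be greater reader confidence.

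**Conclusion.** The concern holds and must be fixed. As written, the test cannot compare the modalities, and its conclusion in favour of s-HCT is effectively settled before any data are read. With complete data on 50 patients it must reject for any mean score above about 5.2% (one-sided) or 7.3% (two-sided), whatever the variability. The simulated 100% rates, against a nominal 5%, agree with this but rest on assumed SDs. The rule is wrong as written, not merely short of detail. The damage is confined to the secondary reader-confidence objective.

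**What to change.** In Section 7.3:

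- Define the outcome as the s-HCT score minus the conventional score for the same reader and patient, separately for hemorrhage and fracture.
- Keep the grand-mean model with its patient random intercept. Add a reader random effect and small-sample degrees of freedom (for example Satterthwaite), because there are only five readers.
- State whether the test is one- or two-sided, and report the mean difference with its 95% CI.
- Conclude more confidence with s-HCT only if the mean difference is positive and significant.

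If both raw scores are modelled with a modality fixed effect instead, include patient-by-modality and reader-by-modality random effects. A patient intercept alone does not control the error rate. The same edit should say what the confidence score means.

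The cost is a sentence or two and no new data, since the same readers already score both modalities. The price of the reader effect is precision: under the first set of assumed SDs, the 95% CI half-width grows from about 4.4 to about 8.0 points (median over simulated trials; mean 8.4).
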